10.2 Sample Size Calculation

10.2.1 N Calculated

Number of planned patients: 60 evaluable patients (both eyes) per arm

Total N = 180 patients

10.2.2 Justification for sample calculation

Sample size calculation was performed based on the results of the phase IV, multicenter, prospective, double-blind, randomized efficacy and safety clinical study of Humylub Ofteno® PF ophthalmic solution, versus Systane® Ultra and Systane® Ultra preservative free performed in subjects diagnosed with mild to moderate dry eye. The reduction in the mean score of the OSDI test was considered as the main efficacy variable, with a dosage of 1 drop QID. In this study, after one month of treatment, subjects assigned to Humylub Ofteno® PF had a decrease of -49.3% vs -41.3% for Systane Ultra and -48.3% for Systane Ultra PF, with respect to their initial mean values with no statistical differences between treatments ($p>0.05$) [57].

For the present protocol, it is expected that, after 3 days of treatment, 30% of subjects treated with Humylub Ofteno® PF will have a 35% decrease in OSDI score compared to their initial mean value.

The sample size was calculated using the equation for two proportions [58], considering a power of 80% (β), a significance level of 0.05 (α) and a margin of non-inferiority (δ) of 10% and based on the following working hypotheses:

$$H_0: P_A - P_B \leq \delta$$

$$H_1: P_A - P_B > \delta$$

Where, δ is the margin of non-inferiority and, the ratio between the sample size of the two groups is:

$$k = \frac{\eta A}{\eta B}$$

Equations

The calculation to estimate sample size and power was performed using an online tool and following the equations: [59]

$$n_A = kn_B \text{ y } n_B = \left(\frac{P_A(1 - P_A)}{k} + P_B(1 - P_B) \right) \left(\frac{z_{1-\alpha} + z_{1-\beta}}{p_A - p_B - \delta} \right)^2$$

$$1 - \beta = \Phi(z - z_{1-\alpha}) + \Phi(-z - z_{1-\alpha}) \text{ , } z = \frac{P_A - p_B - \delta}{\sqrt{\frac{P_A(1 - P_A)}{n_A} + \frac{P_B(1 - P_B)}{n_B}}}$$

$$k=nA/nB$$

Φ is the standard normal distribution function

Φ^{-1} is the standard normal quantile function

α is a Type I error,

β is the Type II error, which means that $1-\beta$ is the power, and

δ is the test margin.

According to the previous calculation, the result was 50 subjects, this calculation was increased by 20% considering possible losses (10 subjects). The total suggested sample size is 180 subjects (60 cases per arm), which will provide both eyes for the study.

11. Ethical considerations

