3.1 Primary objective

To demonstrate the non-inferiority of Humylub Ofteno® PF compared to Hyabak® and Lagricel Ofteno® PF in the efficacy of the treatment of patients with dry eye, by means of the OSDI (Ocular Surface Disease Index) test score.

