3.3 Hypothesis

H_0 = The Humylub Ofteno® PF ophthalmic solution is not inferior in its efficacy compared to its comparators, after 30 days of treatment, presenting a 35% decrease in the final score of the OSDI test compared to its initial value in at least 30% of exposed patients.

$$H_0: P_A - P_B \leq \delta$$

H_1 = The Humylub Ofteno® PF ophthalmic solution is inferior in its efficacy compared to its comparators, after 30 days of treatment, as it does not present a 35% decrease in the final score of the OSDI test compared to its initial value in at least 30% of exposed patients.

$$H_1: P_A - P_B > \delta$$

4. Study design

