10.1.2 Data Interpretation

The Kolmogorov-Smirnov and Shapiro Wilk tests will be performed, as applicable, to determine if the distribution of the data is normal in the results obtained in each study group [56].

The results of the continuous quantitative variables will be presented in measures of central tendency: mean, standard deviation, standard error and/or ranges.

- Intra-group analysis: For equal variances, Tukey's POST-HOC test will be used, otherwise the Dunnett statistic will be used. One-way analysis of variance (one-way ANOVA) will be used when applicable.
- Intergroup analysis: Differences between groups will be analyzed using the Repeated Measures Analysis of Variance (ANOVA) test or the Student's t-statistic when applicable.

A non-inferiority margin (δ) of 10% will be used for the primary efficacy endpoint, based on the primary endpoint of the study. The level of difference to consider significance will be an alpha (α) of 0.05 or less.

The result of the nominal and ordinal qualitative variables will be presented in frequencies, proportions and/or percentages.

The statistical analysis to identify significant differences in the qualitative variables will be carried out by creating 2x2 contingency tables and will be carried out as follows:

- Intra-group difference: McNemar test. This is applied to 2x2 contingency tables with a dichotomous feature, with pairs of paired subjects, to determine if the marginal frequencies of row and column are equal (marginal homogeneity) [7].

- Difference between groups: Pearson's X² (Chi-square) test or Fisher's exact test at expected values less than 5.

The level of difference to consider significance will be an alpha (α) of 0.05 or less.

For the reporting of adverse events, all subjects who were randomly assigned to an intervention group after baseline (intention-to-treat population, ITT) will be considered.

The final report of the results will be shown in tables or graphs, as appropriate.

Variable Type	Variable	A1	B1	B2	C1	D1	D2	D3	D4	E1	E2
Background											
A1	Demographic	DT									
Basal											
B1	Medical History/Selection Criteria	DT									
B2	Comprehensive ophthalmological evaluation	DT				TB	T	T	T	TB	TB
Efficiency											
C1	OSDI	DB			B					TB	
Secondary efficacy outcome											
D1	TRLNI				DB	B				TB	
D2	Corneal and conjunctival stains (TVL and TF)		DT	DT			TB			TB	
D3	Conjunctival Hyperemia		DT	DT		TB				TB	
D4	Chemosis		DT	DT		TB				TB	
Safety											

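### The 80% power in 10.2.2 is at most power for one pair of arms, while the primary objective claims non-inferiority to both Hyabak and Lagricel and no decision rule is stated

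*Combined protocol and SAP*

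**What the plan says.** The primary objective (3.1) names two products joined by *and*: "To demonstrate the non-inferiority of Humylub Ofteno® PF compared to Hyabak® and Lagricel Ofteno® PF in the efficacy of the treatment of patients". The hypothesis (3.3) speaks of comparators in the plural, saying that Humylub "is not inferior in its efficacy compared to its comparators, after 30 days of treatment", but the accompanying expression has a single contrast, P_A − P_B.

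Section 10.2.2 uses a two-group formula: "The sample size was calculated using the equation for two proportions [58], considering a power of 80% (β"), with α of 0.05 and a margin of 10%. The formula contains z at 1−α, so the test is one-sided at 0.05. The only responder rate given is for the test product: "30% of subjects treated with Humylub Ofteno® PF will have a 35% decrease in OSDI score". No rate is given for Hyabak or Lagricel. The result is 50 per arm, raised by 20% to 60, for 180 patients in three arms.

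The evaluable number is stated in two ways. The synopsis and 10.2.1 plan 60 evaluable patients per arm, whereas 10.1.4 says that 50 evaluable per arm are required.

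Section 10.1.2 gives the margin and alpha for the primary endpoint. Neither it nor any other section says how the Hyabak and Lagricel comparisons combine into one conclusion, gives a testing order, or quotes power for the two comparisons together.

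**The concern.** A sample size from a two-group formula carries the power of one comparison. The objective, read in the ordinary way, needs two comparisons to succeed, and the chance of that is lower unless one of them is nearly certain. The 80% is therefore quoted for a narrower claim than the one the trial makes.

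The unstated rule matters as well. Suppose the interval clears the margin against one product only. If both are required, the primary objective has failed. If one is enough, the trial is a success. The study is open-label (4.1) and the sponsor's own staff run the analysis (10.1.1), so the rule should be written down before data are seen.

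**Working it through.** **Inputs.** From 10.2.2: Humylub responder rate P_A = 0.30; margin 0.10; one-sided α = 0.05 (z = 1.6449); power 0.80 (z = 0.8416); 50 per arm calculated and 60 planned; equal arms. The comparator rate P_B is not in the documents. I assume 0.30 for both comparators and show a range.

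**1. The plan's own figure.** At equal rates the formula in 10.2.2 gives

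n = (0.30×0.70 + 0.30×0.70) × (1.6449 + 0.8416)² / 0.10² = 0.42 × 6.1826 / 0.01 = 259.7, so 260 per arm.

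The stated 50 does not reproduce. Reaching 50 takes an input that the plan does not state, for example P_B of about 0.187 (a comparator some 11 points worse than Humylub) or a margin of about 0.23 at equal rates.

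**2. What 80% per pair would mean for both, if it were true.** The two test statistics share the Humylub arm. With equal arm sizes and rates their correlation is 0.5.

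- 80% per pair at 50 per arm: P(both) = Φ₂(0.8416, 0.8416; 0.5) = 0.687. With no correlation it would be 0.80² = 0.64.
- The same assumption with all 60 evaluable: 2.4865 × √(60/50) − 1.6449 = 1.079. This gives 0.860 per pair and 0.772 for both.
- Unequal comparators: at 260 per arm, with Humylub 30%, one comparator 30% and the other 25%, the pairs have 80.0% and 98.6%, and both succeed 79.6% of the time.
- For 80% on both at equal rates, each pair needs 87.9%, which takes about 1.28 times the sample size.

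**3. Power from the stated inputs.** Per pair, power = Φ[(P_A − P_B + 0.10)/SE − 1.6449], with SE = √[(P_A(1−P_A) + P_B(1−P_B))/n].

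- P_B = 0.30, n = 50: SE = √(0.42/50) = 0.0917; 1.091 − 1.645 = −0.554; power 0.290 per pair and 0.149 for both.
- P_B = 0.30, n = 60: SE = 0.0837; 1.195 − 1.645 = −0.450; power 0.326 per pair and 0.177 for both.
- Simulation of the Wald test (200,000 runs) gave 29.6% and 14.9% at 50, and 33.1% and 17.2% at 60.

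Range over the missing P_B, taken as the same for both comparators:

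| P_B | 50 per arm: pair / both | 60 per arm: pair / both |
|---|---|---|
| 0.35 | 13% / 5% | 15% / 5% |
| 0.30 | 29% / 15% | 33% / 18% |
| 0.25 | 51% / 35% | 58% / 42% |
| 0.20 | 75% / 63% | 82% / 72% |

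At P_B = 0.30, 80% per pair needs about 260 per arm and 80% for both about 333.

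**4. Why the rule should be fixed in advance (illustration only; no section proposes these rules).** If success against either product were enough and both comparators were exactly 10 points better, the false-claim rate would be 1 − Φ₂(1.645, 1.645; 0.5) = 8.8%. Simulation at 60 per arm, 30% against 40%, gave 9.2%. If the comparators were pooled, with Humylub 30% and comparators 30% and 40%, non-inferiority would be declared about 16% of the time although Humylub sits on the margin against one of them.

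**The case against.** The strongest reply is that the products are joined by *and*, so the ordinary reading is that both must be met. Each test can then run at full alpha without inflating the false-claim rate. On that reading what is missing is a sentence and a label, and quoting power per comparison is common practice. Much of this stands: no section proposes an either-one or pooled rule, so the 8.8% and 16% figures describe rules the plan does not contain. What does not stand is leaving the 80% unlabelled beside a two-comparator objective, or leaving the rule to be inferred.

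Three stronger readings are tempting and are not supported:

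- A reader might infer that the trial's power is 69%. That figure is conditional on 80% per pair, which the stated inputs do not give, and on equal comparator rates, which the documents do not state. It also depends on whether 50 or 60 patients per arm are evaluable.
- A reader might infer from 10.1.2 that the primary claim will be tested by Tukey comparisons across all three pairs. Tukey is listed there under intra-group analysis and is not offered as the non-inferiority test.
- A reader might take the analysis "carried out by creating 2x2 contingency tables" as the primary test. That sentence concerns qualitative variables, whereas 7.4.4 classes OSDI as continuous and assigns it ANOVA. How well those methods fit a responder hypothesis is a different question.

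**Conclusion.** The point holds. Section 10.2.2 sizes one contrast and applies the result to three arms, while 3.1 and 3.3 claim non-inferiority to two comparators without a stated rule. The 80% is at most power per comparison.

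If it were true at 50 evaluable per arm, power for the stated objective would be about 69%, or about 77% with 60 evaluable. Both figures assume equal comparator rates and a correlation of 0.5. The shortfall almost disappears if one comparator's rate is about 5 points lower than the other's.

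The larger gap lies in the starting figure. With an assumed comparator rate of 0.30, power is about 29% per pair and 15% for both at 50 per arm, and 33% and 18% at 60. Those values move a good deal with the comparator rate, which is why it has to be stated. Supplying it would not by itself settle the decision rule or turn a per-pair power into a joint one.

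**What to change.** In 3.3 and 10.1.2, state that non-inferiority is concluded only if it is shown separately against Hyabak and against Lagricel, each at the full one-sided alpha and with no pooling of comparators. Add that if only one comparison is met, the conclusion names that comparator alone.

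In 10.2.2, label the power as per comparison and report beside it the joint power for both. Compute each from a stated comparator rate and the evaluable number actually intended, after reconciling 50 in 10.1.4 with 60 in 10.2.1. Do not insert 69% as the trial's power, since it would rest on an 80% that does not reproduce.

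The cost is wording, and the quoted power becomes less favourable. These changes need no extra patients. Whether the sample is large enough is a separate decision, which the recomputed figures will put in view.

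### The trial is sized for a one-sided 5% non-inferiority test, but the analysis section names only tests of equality and no sidedness or interval level, so the stated 80% power belongs to no analysis in the plan.

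*Combined protocol and SAP*

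**What the plan says.** **Sizing (10.2.2).** The calculation is for two proportions, "considering a power of 80% (β), a significance level of 0.05 (α) and a margin of non-inferiority (δ) of 10" per cent. The numerator of the printed formula is "z_{1-\alpha} + z_{1-\beta", so alpha is not halved. The hypotheses are directional and set against a margin: "H_0: P_A - P_B \leq \delta". For the test arm, the expectation is that "30% of subjects treated with Humylub Ofteno® PF will have a 35% decrease in OSDI score compared to their initial mean value". No responder proportion is given for either comparator. The supporting data are mean score reductions from an earlier study, in which the test product "had a decrease of -49.3% vs -41.3% for Systane Ultra and -48.3% for Systane Ultra PF". On the number, "the result was 50 subjects, this calculation was increased by 20% considering possible losses (10 subjects"), and "The total suggested sample size is 180 subjects (60 cases per arm").

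**Analysis (10.1.2 and the variable table in 7.4.4).** Section 10.1.2 repeats the 10% margin for the primary endpoint and adds: "The level of difference to consider significance will be an alpha (α) of 0.05 or less". The between-group methods it names are repeated-measures ANOVA or Student's t for quantitative variables, and Pearson chi-square or Fisher's exact test for qualitative ones. The table in 7.4.4 assigns the OSDI score to repeated-measures and one-way ANOVA. No confidence interval, confidence level, sidedness or margin-based test appears.

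**Evaluable numbers.** Section 10.1.4 requires 50 evaluable patients per arm. The synopsis and 10.2.1 plan 60.

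**The concern.** A power figure has meaning only for a stated decision rule. Section 10.2.2 implies one: reject inferiority if a one-sided 5% test against the margin succeeds, which is the same as using the bound of a 90% interval. Section 10.1.2 does not carry that rule over. Its tests ask whether the arms differ at all. A non-significant ANOVA or chi-square result does not show non-inferiority, and a significant one does not settle whether the difference lies within 10 points.

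Two things are at stake. An analyst who follows 10.1.2 exactly could not deliver the primary objective. An analyst who supplies the missing margin test would have to choose its level, possibly after seeing the data, and a 90% and a 95% interval can give opposite answers near the margin.

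**Working it through.** **Inputs.** From 10.2.2: alpha 0.05, power 80%, margin 0.10, test-arm responder rate 0.30, 50 per arm rising to 60. Equal allocation follows from 60 per arm. Normal quantiles: z(0.95) = 1.645, z(0.975) = 1.960, z(0.80) = 0.842. The comparator rate is not given.

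**1. Which critical value gives 50?** With d the assumed difference in favour of the test arm, the formula for equal arms is n = [P_A(1−P_A) + P_B(1−P_B)] × [(z_α + z_β)/(d + margin)]².

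- *Stated 30% rate, assumed equal in both arms:* the variance term is 2 × 0.30 × 0.70 = 0.42. One-sided 5% gives 0.42 × (2.486/0.10)² ≈ 260 per arm, and one-sided 2.5% gives 0.42 × (2.802/0.10)² ≈ 330. Neither is 50.
- *Other percentages in 10.2.2 read as proportions, 0.493 and 0.35:* the variance term is 0.2500 + 0.2275 = 0.4775, and d + margin = 0.143 + 0.10 = 0.243. One-sided 5% gives 49.99, which matches the plan's 50. One-sided 2.5% gives 63.5, i.e. 64.

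The match supports 1.645 as the value used, in line with the printed formula. The pair was found by trying the percentages in that section. The plan does not label them as P_A and P_B, so this is an inference.

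**2. Effect of the interval level.** Suppose 50 per arm does give exactly 80% at one-sided 5%. The standardised distance is then 1.645 + 0.842 = 2.486, whatever the rates.

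| Evaluable per arm | One-sided 5% (90% interval) | One-sided 2.5% (95% interval) |
|---|---|---|
| 50 | 80% | Φ(2.486 − 1.960) = 70.1% |
| 60 | Φ(2.486 × √1.2 − 1.645) = 86.0% | Φ(2.486 × √1.2 − 1.960) = 77.8% |

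Holding 80% at the 95% level would take a factor (2.802/2.486)² = 1.27, or 50 × 1.27 = 63.5, i.e. 64 per arm.

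**3. Power of a test the plan does name.** With the inferred pair 0.493 and 0.35, a two-sided 5% chi-square test of equality has about 30% power at 50 per arm. That is a different quantity, because the test contains no margin.

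**4. Sensitivity to the rates.** With 30% in both arms, the standard error at 50 per arm is √(0.42/50) = 0.0917, and 0.10/0.0917 = 1.091. Power is Φ(1.091 − 1.645) = 29.0% at one-sided 5% and Φ(1.091 − 1.960) = 19.2% at one-sided 2.5%.

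**5. Both comparators.** Sections 3.1 and 3.3 name both comparators together. The shared test arm makes the two comparisons correlated; 0.5 is assumed here. If both must succeed, joint power from the bivariate normal is 68.7% when each comparison has 80%, and 55.8% when each has 70.1%.

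**The case against.** The strongest reply is that the plan contains no contradiction about sidedness. The hypotheses are directional, a margin is stated, and the formula is one-sided. An alpha of 0.05 in 10.1.2 is compatible with a one-sided 5% margin test, and no section says two-sided, 0.025 or 95% interval. This stands: the formula is the only evidence on sidedness for the margin comparison, and it points to one-sided 5%.

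A reader might infer that the plan's own significance rule cuts the 80% to about 70%. The documents do not support that. The value 1.960 would be the reader's addition. The 70% is the power of a margin test at the 95% level, which the plan does not name, and it is not the power of ANOVA or chi-square. It also takes 50 evaluable per arm, where the synopsis and 10.2.1 plan 60. And it treats the 80% as sound, which the stated 30% rate with equal arms does not bear out.

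The reply does not remove the gap. One-sidedness appears only through the sizing hypotheses and a formula subscript. The analysis section neither repeats it nor names any test that uses the margin.

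**Conclusion.** The concern holds as a mismatch between sizing and analysis. The sponsor's critical value is not an arithmetic error. The 80% belongs to a one-sided 5% margin test that 10.1.2 and 7.4.4 do not specify, and the tests they do specify cannot answer the primary question.

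The size depends on how the gap is filled. At one-sided 5%, the stated power is unchanged by this point. At the 95% level it is about 70% with 50 evaluable per arm and 78% with 60. Both figures assume that the undisclosed rates truly give 80% at 50 per arm. Only the factor 1.27 is free of that assumption; the absolute power figures are not, and with 30% in both arms they fall to about 29% and 19%. The joint figures add two further assumptions: that both comparators must be met, and a correlation of 0.5.

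**What to change.** 1. In 10.1.2, name the primary test: a confidence bound for the difference in responder proportions (test product minus comparator), set against the 10% margin, separately for each comparator. Align the OSDI row in 7.4.4 with it. ANOVA and chi-square can stay as descriptive or secondary comparisons.
2. State one error rate in both 10.1.2 and 10.2.2. Either declare one-sided 0.05 with a 90% interval, which matches the printed formula, or declare one-sided 0.025 with a 95% interval and restate the power.
3. In 10.2.2, state P_A and P_B for each comparison and recompute the power from them. The 70% and 78% above should not be copied into the protocol before that is done.
4. Say whether non-inferiority must be shown against both comparators. If so, give the joint power: about 69% at one-sided 5% if each comparison has 80% and the correlation is 0.5.

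Items 1 and 2 are wording changes in three sections and need no added patients. The cost is that the stated power may become less favourable. Whether the sample size is adequate can be judged only after item 3.

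### The power equation in section 10.2.2 adds the opposite tail to a one-sided test; with an unsigned margin and no stated comparator rate, it cannot expose a wrong-direction input

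*Combined protocol and SAP*

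**What the plan says.** The synopsis, section 3.3 and section 10.2.2 all give the alternative in symbols as "H_1: P_A - P_B > \delta". Section 10.2.2 lists the design inputs as "considering a power of 80% (β), a significance level of 0.05 (α) and a margin of non-inferiority (δ) of 10"%, with no sign on the margin. Its sample-size equation is one-sided, with the factor "z_{1-\alpha} + z_{1-\beta}}{p_A - p_B - \delta" squared. Its power equation is "\Phi(z - z_{1-\alpha}) + \Phi(-z - z_{1-\alpha"), where z is the distance P_A - P_B - delta divided by an unpooled standard error. These equations are the declared method: "The calculation to estimate sample size and power was performed using an online tool and following the equations".

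The only responder rate supplied is for the test product: "30% of subjects treated with Humylub Ofteno® PF will have a 35% decrease in OSDI score". No comparator rate appears anywhere, and the letters A and B are not assigned to products. The outcome is reported as "the result was 50 subjects, this calculation was increased by 20% considering possible losses (10 subjects"), and then "The total suggested sample size is 180 subjects (60 cases per arm").

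In words, the synopsis and section 3.3 attach non-inferiority to H0 and inferiority to H1.

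**The concern.** For the alternative P_A - P_B > delta tested at z(1-alpha), power is the single term Φ(z - z(1-alpha)). The added term is the probability of landing far below delta, which is evidence against the alternative. The sum is the power of a two-sided test of P_A - P_B = delta with alpha in each tail.

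In a plan with a signed margin and both rates stated, this would be a cosmetic slip. Here neither the sign of delta nor the comparator rate is given, so a power check is where a sign error should show up as power close to zero. The second term removes that signal: the printed equation gives the same value for z and for -z. A committee reading 10.2.2 cannot tell whether the planned arms were sized for the question the trial asks.

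**Working it through.** **Inputs.** From 10.2.2: alpha 0.05, so z(0.95) = 1.645; power 0.80, so z(0.80) = 0.842; P_A = 0.30; margin 10%; equal allocation; 50 per arm, raised to 60. Assumptions: A is Humylub, because 30% is stated for Humylub; P_B = 0.30, the usual planning case for non-inferiority. Other values of P_B are solved for below. Both 50 and 60 are evaluated because section 10.1.4 requires 50 evaluable patients per arm and section 10.2.1 plans 60.

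**1. The plan's own figure.** Printed equation: n = [P_A(1-P_A) + P_B(1-P_B)] × [(1.645 + 0.842)/(P_A - P_B - delta)]².

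- With P_A = P_B = 0.30 and delta of either sign: n = 0.42 × (2.4865/0.10)² = 259.7, so 260 per arm. The stated 50 is not reproduced.
- Solving for the P_B that gives n = 50 at P_A = 0.30: about 18.8% or 63.4% if delta = -0.10; about 2.9% or 43.7% if delta = +0.10. None of these rates is in the documents.
- Check at delta = -0.10, P_B = 0.188: variance sum 0.21 + 0.1527 = 0.3627; distance 0.212; n = 0.3627 × (2.4865/0.212)² = 49.9.

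**2. Printed power against one-sided power.** z = (P_A - P_B - delta)/SE, with SE = √(0.42/n) at equal 30% rates. At n = 50, SE = 0.0917. At n = 60, SE = 0.0837.

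| Case | z | Printed, two terms | One-sided, first term |
|---|---|---|---|
| Correct-direction 80% design point | 2.486 | 0.80002 | 0.80000 |
| At the margin | 0 | 0.100 | 0.050 |
| delta = -0.10, 30% vs 30%, n = 50 | 1.091 | 0.293 | 0.290 |
| delta = -0.10, 30% vs 30%, n = 60 | 1.195 | 0.329 | 0.327 |
| delta = +0.10, 30% vs 30%, n = 50 | -1.091 | 0.293 | 0.003 |
| delta = +0.10, 30% vs 30%, n = 60 | -1.195 | 0.329 | 0.002 |

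The third and fifth rows show the problem. Changing the sign of delta turns a non-inferiority test into a test that A beats B by more than 10 points. The first-term power falls from 29.0% to 0.3%, while the printed value stays at 29.3%.

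**3. Symbols against words.** With A = Humylub and delta = -0.10, the printed symbols describe a proper non-inferiority test, but the words for H0 and H1 are then the wrong way round. With A = comparator and delta = +0.10, the symbols match the words, but rejecting H0 would then demonstrate inferiority. Under neither reading do symbols and words together give a non-inferiority test.

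**The case against.** The strongest reply is that no planned number rests on the extra term. The sample-size equation does not contain it, 80% power is an input and not an output, and deleting the term leaves 50, 60 and 180 unchanged. With the margin signed correctly and equal 30% rates, the term adds 0.3 percentage points. All of that stands.

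Three stronger readings are tempting and should not be drawn:

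- **That the trial runs at a 10% type I error.** The printed equation does return 10% at the margin, but it is a planning formula. The error rate depends on the analysis in section 10.1.2, which does not use it. That section sets alpha at 0.05 and gives no one-sided non-inferiority test or confidence-interval rule.
- **That 50 per arm came from a wrong-direction comparator rate.** Rates of 43.7% (delta = +0.10) or 63.4% (delta = -0.10) would give 50 in the wrong tail, where one-sided power is about 0.002%. They are back-solved values, and nothing shows that the sponsor entered them.
- **That squaring the distance in the sample-size equation is an error.** It is standard for normal-approximation formulas. Direction has to come from the inputs, which is why the inputs must be stated.

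It is also fair to say that the larger difficulty is the missing comparator rate and the unreproduced 50. The extra term did not cause either.

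**Conclusion.** The mismatch is real. A directional alternative with a one-sided critical value is paired with a two-tailed power expression, and nothing in 10.2.2 explains or limits the second term. Taken alone it is negligible. Combined with an unsigned margin and an unstated comparator rate, it means the printed calculation cannot reveal a wrong-direction input: 29.3% printed against 0.3% in the H1 direction, for delta = +10%, equal 30% rates and 50 per arm.

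The practical consequence is the power statement. If the comparator rate is also 30%, one-sided power in the non-inferiority direction is about 29% at 50 per arm and 33% at 60, against the stated 80%. A claim of 80% at 50 per arm in that direction requires a comparator rate of about 18.8%, which puts Humylub roughly 11 points ahead (30 - 18.8 = 11.2). These figures rest on A being Humylub, the unpooled normal approximation that the plan prints, and comparator rates that are assumed or back-solved because the documents give none.

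**What to change.** 1. In 10.2.2, delete the second term so that power = Φ(z - z(1-alpha)).
2. In the same place, define A as Humylub, B as the comparator and delta as -0.10. Carry the signed margin into the synopsis, section 3.3 and section 10.1.2.
3. In the synopsis and section 3.3, exchange the verbal H0 and H1, so that H0 is inferiority by the margin or more and H1 is non-inferiority. Correcting 10.2.2 alone would leave words and symbols in conflict.
4. State the assumed P_B and its basis, and confirm that P_A - P_B - delta is positive before applying the sample-size equation.
5. Restate the one-sided power at 50 and at 60 evaluable patients per arm.

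The cost is text in four sections and one restated figure. The correction itself requires no extra patients, but the stated power will probably be less favourable: about 29% and 33% if P_B is 30%. Whether to enlarge the trial, to 260 per arm for 80% power under that assumption, is a separate decision that the corrected figure would inform.
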